## 4.5 Screen Failure

A subject who signs an informed consent form (ICF) and does not have a CorPath GRX endovascular procedure or is enrolled in the study but withdraws their consent will be considered a screen failure. However, all data collected from the enrolled subject prior to the time of consent

*Version Date: May 21, 2021*

*This confidential document is the property of Corindus, Inc. and shall not be reproduced, distributed, disclosed or used without the express written consent of Corindus, Inc.*

withdrawal will be included in the analysis.

#### **4.6 Patient Selection**

Subjects with a clinical indication for endovascular coil and/or stent-assist coiling embolization of unruptured cerebral aneurysms. Subjects who meet all inclusion criteria while exhibiting none of the exclusion criteria (see below) and have signed the informed consent will be considered enrolled. All eligible subjects will be evaluated using the Corindus CorPath® GRX System in Endovascular Embolization Procedures of Cerebral Aneurysms.

##### **4.6.1 INCLUSION CRITERIA**

1. Age  $\geq$  18 years.
2. At least one cerebral aneurysm (unruptured) with indication for endovascular treatment; dome to neck ratio  $>1.5$  or aneurysm neck width  $>4.0$  mm.
3. The Investigator deems the procedure appropriate for both manual or robotic-assisted endovascular treatment.
4. The conscious subject has been informed of the nature of the study, agrees to its provisions and has provided written informed consent.

##### **4.6.2 EXCLUSION CRITERIA**

1. Failure / unwillingness of the subject to provide informed consent, unless the EC has waived informed consent.
2. The Investigator determines that the subject or the neurovascular anatomy is not suitable for robotic-assisted endovascular treatment.
3. Women who are pregnant.
4. Persons under guardianship or curatorship.

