#### 3.2 Primary Effectiveness Endpoint

The primary effectiveness endpoint will be defined as successful completion of the robotic-assisted endovascular procedure absent any unplanned conversion to manual for guidewire or microcatheter navigation, embolization coil(s) or intracranial stent(s) deployment, or an inability to navigate vessel anatomy.

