This discussion should highlight the fact that the patient is being asked solely to share the data collected from their endovascular robotic procedure and any related events through 24-hours post-procedure or discharge, whichever occurs first. The study investigator and/or staff are responsible for obtaining written informed consent from each potential subject before any study specific procedures required by the protocol are performed. Informed consent should be obtained in written format and using a form approved by the EC and Competent Authority. The form should contain standard language consistent with local policies for ensuring privacy of confidential information. All subjects must sign the informed consent prior to any procedures/tests that go beyond initial assessments associated with the standard care for subjects with cerebral aneurysms and before any study related treatment assessments are administered and subject-related health information can be entered into the study database.

Subjects are considered enrolled in the study once the subject signs the study Informed Consent Form. Failure to obtain signed informed consent, renders the subject ineligible. For those subjects that sign informed consent, a copy shall be kept in the subject's medical records and study files. A copy of the fully executed informed consent form must be given to each subject enrolled in the study.

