#### 4.8.5 CorPath GRX Endovascular Procedure Workflow

The protocol allows for the Investigator to perform the following with the CorPath GRX System:

- Navigate a 0.014" guidewire in the neurovascular anatomy;
- Navigate a microcatheter into the neurovascular anatomy robotically;
- Navigate a microcatheter to the aneurysm robotically;
- Navigate treatment devices (coils/stents) to the aneurysm robotically;
- Deploy treatment devices into the aneurysm robotically.

The Investigator should refer to the CorPath GRX System Operator's Manual for a detailed description of the system and relevant techniques.

After arterial access is obtained, the Investigator will specify what devices will be used robotically prior to starting the robotic portion of the endovascular procedure.

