## 6. STATISTICAL CONSIDERATIONS AND ANALYSIS

Data for subjects that undergo an endovascular procedure where the Corindus GRX device is used (or attempted to be used) will be included in both primary and secondary endpoints where data are available.

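### A committee-approved patient given up on for anatomy after arterial access but before robotic use drops out of the primary effectiveness denominator, while the same anatomy counts as a failure once the robot is used

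*Protocol*

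**What the plan says.** **Anatomy as an exclusion.** Protocol 4.6.2, exclusion 2: "The Investigator determines that the subject or the neurovascular anatomy is not suitable for robotic-assisted endovascular treatment". The criterion carries no time limit. Protocol 4.6.3 puts confirmation of the eligibility criteria into the evaluation submitted to the Eligibility Committee, which decides before treatment. The Schedule of Activities marks the eligibility check only under Pre-Procedure.

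**Anatomy as a failure.** Protocol 3.2 and SAP 4.2 count unplanned conversion to manual as failure of the primary effectiveness endpoint, "or an inability to navigate vessel anatomy".

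**Who is analysed.** Protocol 4.4: "Subjects are considered enrolled in the study once the subject signs the study Informed Consent Form". Protocol 4.5 defines a screen failure to include "A subject who signs an informed consent form (ICF) and does not have a CorPath GRX endovascular procedure". Protocol 6 takes subjects "where the Corindus GRX device is used (or attempted to be used) will be included in both primary and secondary endpoints". SAP 4.1 defines the Analysis Cohort by an attempted procedure, identified by a recorded robotic microcatheter insertion time. SAP 4.2 uses that cohort for the primary effectiveness endpoint.

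**Order of events.** Protocol 4.8.5: "After arterial access is obtained, the Investigator will specify what devices will be used robotically prior to starting the robotic portion". In the recommended technique, access and guide catheter placement are manual (steps 1 to 4) and the robotic devices are named at step 5. The microcatheter and wire are inserted by hand (steps 6 and 7), the microcatheter insertion time is recorded (step 8), and the cassette is loaded (step 9). Protocol 4.8.6 documents an unplanned conversion only for a device that has been used robotically.

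**The concern.** Between arterial access and first robotic use, the unmasked operator has already worked through the proximal vessels and can still decide against the robot. A patient treated manually from that point because of anatomy had no CorPath procedure and may have no insertion time. Such a patient is a screen failure and is outside the Analysis Cohort. If the operator had started robotically and then stopped for the same anatomy, the patient would be a primary failure. The timing of one person's decision thus settles whether a case is counted as a failure or not counted at all.

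The cases most likely to be lost this way are those most likely to fail, so the bias runs towards success. The trial has no control arm in which the same selection would operate. The loss could also go unseen, because the additional summaries in SAP 4.5 list neither screen failures nor subject disposition.

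**Working it through.** **1. Follow one patient through the rules.** The patient has consented, has been approved by the committee and has arterial access for a planned CorPath case. The operator stops for anatomy at one of three stages.

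| Stopped at | Protocol 4.5 | Protocol 6 | SAP 4.1 cohort | Primary effectiveness |
|---|---|---|---|---|
| Steps 1-5 (manual access, guide catheter, devices named) | screen failure | robot not used or attempted: out | no insertion time: out | not counted |
| Steps 6-9 (manual microcatheter, time recorded, cassette loaded) | unclear | depends on what *attempted* means | in if the step 8 time is the one meant | unclear |
| After robotic use begins | not a screen failure | in | in | failure |

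The middle row is unclear because the step 8 time follows a manual insertion and precedes cassette loading, yet the SAP calls it robotic. Protocol 6 uses a different test, whether the device was used or attempted.

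**2. Reproduce the plan's figure.** Inputs from Protocol 6.5 and 6.6: p0 = 0.80, p1 = 0.90, two-sided 95% interval (one-sided 0.025), power 80%.

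n = [(1.960·√(0.80·0.20) + 0.842·√(0.90·0.10)) / 0.10]² = [(0.7840 + 0.2525)/0.10]² = 107.4, which rounds up to 108, as planned. Normal-approximation power at 108 is 80.3%.

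Under the exact (Clopper-Pearson) rule, 94/108 has a lower limit of 79.2% and fails; 95/108 has 80.3% and passes. The pass mark is therefore 95. The exact one-sided error is P(X ≥ 95 | 108, 0.80) = 2.1%, and power is P(X ≥ 95 | 108, 0.90) = 81.0%.

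**3. Return k dropped patients as failures.** The documents give no k, so it is an assumption. The plan enrols up to 120 to obtain 108, so within that allowance at most 120 − 108 = 12 could be lost for all reasons together.

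| Result in the cohort | k | Recounted | Exact lower limit | Above 80%? |
|---|---|---|---|---|
| 95/108 (minimum pass) | 0 | 95/108 | 80.3% | yes |
| | 1 | 95/109 | 79.4% | no |
| | 3 | 95/111 | 77.6% | no |
| 97/108 (expected, 0.90 × 108 = 97.2) | 0 | 97/108 | 82.5% | yes |
| | 2 | 97/110 | 80.6% | yes |
| | 3 | 97/111 | 79.7% | no |

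**4. Effect on the false-positive rate.** Let true success among all approved patients with arterial access be 80%, so 20% would fail. If a share f of those failures is dropped before robotic use, success among those analysed is 0.80 / (1 − 0.20f). The chance of passing is P(X ≥ 95 | 108, that rate).

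| f (assumed) | Patients dropped, 0.20f | Rate among analysed | Chance of passing |
|---|---|---|---|
| 0 | 0% | 80.0% | 2.1% |
| 10% | 2% | 81.6% | 5.2% |
| 20% | 4% | 83.3% | 12.0% |

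The nominal one-sided 2.5% is exceeded once about 2 in 100 patients are dropped in this way.

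**The case against.** **Eligibility belongs before the procedure.** Protocol 4.6.3 and the Schedule of Activities place the check there, and no text authorises applying exclusion 2 after sheath insertion. A reader might infer from the criterion's wording that the plan gives the operator an open-ended in-suite exclusion. The documents do not support that reading. What stands against the objection is narrower. No text closes the judgement at approval, and the rules that remove the patient are Protocol 4.5 and SAP 4.1, which apply whatever reason is given. Rewording 4.6.2 alone would not cure this.

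**The window is short.** A reader might also infer that any patient abandoned after arterial access becomes a screen failure. That is too broad: once robotic use begins, the patient is in the cohort and the anatomy counts as a failure. This stands, except that the boundary at steps 6 to 9 is itself unclear.

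**Late surprises should be few.** Three experts with experience of the robot review imaging of the parent vessel and aortic arch, together with the planned devices. This should lower the number of cases, but it does not say how those that occur are classified.

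**The size is uncertain.** One patient reverses the result only at exactly 95/108, which has about a 9% probability if true success is 90%. The removal shares are assumptions. Both points stand.

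**The endpoint measures robotic procedures.** The 90% expectation comes from coronary conversion rates, and the documents do not say whether those denominators include cases never attempted. This is a fair reason to keep the Analysis Cohort as primary and to make the recount a sensitivity analysis.

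Protocol 4.7 says that all data enter summaries, but this does not restore these patients, because SAP 4.2 fixes the primary analysis to the Analysis Cohort.

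**Conclusion.** The gap is real but bounded. As written, Protocol 4.5 and SAP 4.1 remove approved patients abandoned for anatomy after manual access and before robotic use, and the cut between dropped and failed is not tied to one clear event. This can bias the primary proportion upwards.

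The size depends on a number that the documents do not give. One patient is enough to reverse a result at the pass mark, and three are enough at the expected result. A false-positive rate of 2.1% becomes 5.2% or 12.0% if 10% or 20% of failures are lost this way. These figures assume 108 analysed subjects, the exact rule in the SAP, and that every dropped patient would have counted as a failure.

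Nothing in the documents shows that such patients have occurred or that the rule was meant to shed them. The change is a cheap improvement that should be made; the gap does not by itself invalidate the design.

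**What to change.** 1. Define *attempted* by one recorded event and use it identically in Protocol 6 and SAP 4.1.
2. In Protocol 4.5, state that an approved subject who has arterial access for a planned CorPath case and is then treated manually for anatomy or robot suitability is not a screen failure. In 4.6.2, state that the exclusion 2 judgement closes, for classification purposes, before arterial access.
3. Record the time and reason of each such decision, and report the number of approved patients not treated robotically. Protocol 4.8.3 lists access site, planned devices and start time but no such reason, so this is a small eCRF addition.
4. In SAP 4.2, add a pre-specified sensitivity analysis of the primary effectiveness endpoint that counts patients abandoned after arterial access for anatomy or robot suitability as failures. Keep the Analysis Cohort as the primary analysis.

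The operator stays free to treat manually; only the classification changes. The cost is a few sentences, one data item and one analysis, and the success proportion in the sensitivity analysis may be slightly lower.

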##### **4.6.3 Eligibility Committee**

The Eligibility Committee will be responsible for the evaluation of CorPath GRX Neuro subjects for participation in the study. In advance of all study subject enrollment and treatment, the committee will use subject clinical history, Unruptured Intracranial Aneurysm Treatment Score (UIATS) data, the treatment plan, and at least 4 angiographic (DSA or CTA/MRA) images to approve for inclusion into the study or exclude and defer treatment of the cerebral aneurysm with the CorPath GRX

Robotic system.

The Eligibility Committee will be comprised of three neurovascular subject matter experts with experience in the treatment of cerebral aneurysm, data and imaging interpretation, and clinical research trials. They must be neurointerventionalists qualified by training, experience with the CorPath GRX robotic system, and CorPath GRX Neuro Study training.

Once investigative sites are qualified to recruit study subjects, subject imaging, UIATS data, treatment plan, and clinical history will be uploaded to the Oculus Imaging Portal for the committee to review. Neuroimaging will be obtained within 3 months of the eligibility evaluation and will include at least 4 cerebrovascular images with measurements of the targeted cerebral aneurysm, as well as imaging of the parent vessel and aortic arch. Clinical evaluation of patients will include confirmation of all inclusion and no exclusion criteria being met, completion of an UIATS form with applicable treatment justification as needed, and any other applicable medical history required to allow the Eligibility Committee assessment. Additionally, planned procedural devices including Guidewire, Microcatheter, Stent, and Coils will be included.

Upon completion of training on the use of the Oculus Imaging Portal, the Eligibility Committee members will assess the submitted subject data and make a determination on whether a subject qualifies for treatment in the CorPath GRX Neuro Study.

#### **4.7 Subject Withdrawal and Replacement**

Subjects enrolled in the study can discontinue their participation at any time for any reason without prejudice or reduction in the quality of their medical care. The investigator can terminate a subject's participation in the study to protect the subject's health, if the subject fails to follow instructions or if the subject is unable to keep appointments. The Investigator must then document this notification of withdrawal from the study in the appropriate CRF and notify the sponsor. No replacements will be allowed. Up to 120 subjects will be enrolled in order to achieve data on 108 subjects. All data will be included in summaries.

## 4.8 Data to Be Collected

### 4.8.1 Peri-procedural Study Medication Regime

Sites are to follow standard institutional and/or coil/stent manufacturer's guidelines for recommended anticoagulation regimen.

### 4.8.2 Baseline Date

The following baseline data should be collected for all subjects prior to the planned index procedure (usually routinely done for endovascular robotic procedure subjects with cerebral aneurysms):

- Patient Eligibility Criteria
- Head CT angiography or MR angiography
- Demographics
- Medical history
- Pre-endovascular Patient Assessment conducted by a trained person with appropriate qualifications to perform these evaluations:
  - Modified Rankin score
  - Raymond Grade for previously coiled aneurysms
  - National Institutes of Health Stroke Scale (NIHSS) scale
- Laboratory tests, if performed under standard hospital procedure, *should* be collected for all subjects prior to planned index-procedure (usually routinely done for patients undergoing cerebral aneurysm endovascular procedure \*):
  - Hemoglobin (HGB)
  - Hematocrit (HCT)
  - Activated Partial Thromboplastin Time (aPTT)
  - Platelet count
  - International Normalized Ratio (INR)
  - Pregnancy test
  - Serum creatinine
  - Glomerular Filtration Rate (GFR)

**\* Note:** Pre-endovascular Patient Assessment and laboratory tests must be within 7 days of index procedure. Female patients of child-bearing potential must have a negative pregnancy test (serum or urine).

#### 4.8.3 Data Collection Prior To Initiating CorPath Procedure

- Arterial access site
- What devices will be planned for robotic delivery
- Procedure Start Time (Sheath insertion)

#### 4.8.4 Data Collection During CorPath Procedure

- Fluoroscopy time
- Patient radiation exposure (dose-area-product [DAP] and air kerma [AK])
- Aneurysm Assessment
- Contrast volume
- Endovascular procedure End Time (microcatheter out-time)
- Record of all Adverse Events (AE)

**Note:** A de-identified copy of all the procedural angiograms will be sent directly to the imaging core lab.

#### 4.8.5 CorPath GRX Endovascular Procedure Workflow

The protocol allows for the Investigator to perform the following with the CorPath GRX System:

- Navigate a 0.014" guidewire in the neurovascular anatomy;
- Navigate a microcatheter into the neurovascular anatomy robotically;
- Navigate a microcatheter to the aneurysm robotically;
- Navigate treatment devices (coils/stents) to the aneurysm robotically;
- Deploy treatment devices into the aneurysm robotically.

The Investigator should refer to the CorPath GRX System Operator's Manual for a detailed description of the system and relevant techniques.

After arterial access is obtained, the Investigator will specify what devices will be used robotically prior to starting the robotic portion of the endovascular procedure.

#### CorPath Use Technique

*To obtain proper data for analysis, the following procedure, with associated data collection milestones, is recommended, but in no case, dictates use of the CorPath GRX System in a manner*

*Version Date: May 21, 2021*

*This confidential document is the property of Corindus, Inc. and shall not be reproduced, distributed, disclosed or used without the express written consent of Corindus, Inc.*

*different from that presented in the Operator's Manual.*

**The following CorPath Use Technique guides the Investigator through coiling a cerebral aneurysm with the CorPath GRX System.**

1. Obtain arterial access using conventional technique. Record sheath insertion time.
2. Once arterial access is obtained, insert a standard diagnostic catheter using conventional manual technique or guide catheter mounted coaxially over a diagnostic insert catheter.
3. Manually advance the diagnostic select catheter to the parent vessel.
4. Advance guide catheter to desired location in parent vessel and remove wire and diagnostic select catheter. If only diagnostic catheter was used, then remove standard wire and use exchange length guidewire; remove the diagnostic catheter over the exchange wire while maintaining distal wire position. Advance the guide catheter over the exchange wire to the desired location in parent vessel and remove wire.
5. The Investigator will specify which devices will be delivered robotically.
6. Manually advance microcatheter to tip of guide catheter in the parent vessel.
7. Manually insert exchange length guidewire and attach COPILOT bleed back control valve to the microcatheter.
8. Record microcatheter "insertion" time.
9. Load the microcatheter and exchange length guidewire in the CorPath GRX cassette.
10. Using the CorPath System, advance guidewire and microcatheter independently to target treatment area. The Active Device Fixation (ADF) technIQ automated movement can be enabled to keep the guidewire in place during microcatheter movement.
11. With microcatheter in place, remove guidewire.
12. Advance stent into the COPILOT bleed back control valve and proximal microcatheter slowly and according to stent delivery IFU.
13. Place the stent advancement wire into the Device Track of the CorPath GRX.
14. Advance stent, robotically, to target area. The stent will remain completely sheathed in the microcatheter.
15. Robotically position the stent across target aneurysm.
16. Maintaining stent position with CorPath GRX, begin to robotically remove the microcatheter with ADF enabled on the microcatheter. This will unsheathe the stent in place.
17. Using micro-millimeter movements with the CorPath GRX, continue to remove micro-catheter until stent is completely unsheathed and fully deployed.
18. Remove stent deployment shaft robotically, reload exchange length guidewire, and re-advance guidewire to target aneurysm.
19. Using robotic manipulation, advance the microcatheter and guidewire wire to position through the stent struts.
20. Robotically retract guidewire.
21. Remove guidewire from cassette and load embolization coils into Device Track.
22. Using the CorPath System, advance embolization coils to target aneurysm. Slowly deploy embolization coils as per physician preference. The Limited Speed technIQ automated movement may be enabled to slow maximum speed to 6mm/sec if

desired. De- tach and exchange embolization coils as per IFU.

23. After embolization of target aneurysm, robotically remove coil delivery catheter and microcatheter.
24. Perform final control angiography.
25. Record final fluoroscopy time, DAP, AK and contrast volume.
26. Record time of microcatheter “removal” time from the parent vessel.
27. Record Operator pocket dosimeter reading.

#### **4.8.6 Specify Device to Be Used Robotically**

After arterial access prior to using the CorPath GRX System, the Investigator will specify which device he/she will plan to use robotically. If a device that is used robotically cannot be delivered to the target, cross the target or delivered into the target and conversion to manual is needed, it will be documented as an unplanned conversion to manual.

